3.4 RATIONALE FOR STUDY DESIGN

This study is the OLE study of BN29552 (CREAD) and BN29553 (CREAD2), the Phase III, multicenter, randomized, double-blind, placebo-controlled, parallel-group studies of the efficacy and safety of crenezumab in patients with a diagnosis of pAD to mAD.

3.4.1 Rationale for Treatment Duration

AD is a chronic condition with any efficacious therapy likely necessitating many years of treatment. Therefore, it is important to understand the long-term safety of any potential AD treatment beyond the 2-year DBTP in Studies BN29552 and BN29553.

See Section [3.3](#) for information about the end of the study.

3.4.2 Rationale for Long-Term Follow-Up

The primary objective of the study is to evaluate the long-term safety and tolerability of crenezumab. If a patient discontinues treatment early, or if a patient completes the study and does not continue treatment with crenezumab thereafter, assessments performed at 4 and 16 weeks after the last dose of treatment will evaluate the relevant safety parameters over an extended period when no study drug is administered.

Efficacy assessments will allow for the exploration of the long-term effects of exposure to study drug given that continued cognitive decline is expected in this patient population. If a patient discontinues treatment before Week 105, assessments performed at the next annual visit will inform the exploratory efficacy analysis (see Section [1.3.3](#)). For details of the schedule of activities, see [Appendix 1](#).

3.4.3 Rationale for Patient Population

The patient population for this OLE study will comprise patients who completed Week 105 in either Study BN29552 or BN29553 and who meet the inclusion criteria of this Study BN40031 protocol.

3.4.4 Rationale for Safety Outcome Measures

Adverse event data will be gathered in this OLE study, including adverse events related to MRIs (ARIA-E and ARIA-H) to allow collection of long-term safety data in patients who continue to receive crenezumab after completing the main study DBTPs. This data will allow evaluation of the long-term safety and tolerability of exposure to crenezumab in this population. After Week 105 of the OLE study, assessment frequency is reduced to minimize patient burden but to continue safety monitoring. For details of the schedule of activities, see [Appendix 1](#).

3.4.5 Rationale for Exploratory Efficacy Outcome Measures

Efficacy assessments/scales in the OLE replicate those in Studies BN29552 and BN29553, allowing a full profile of efficacy data to be collected for all patients, including those who received placebo in Studies BN29552 and BN29553 but will receive crenezumab 60 mg/kg during the OLE. As with Studies BN29552 and BN29553, assessments in clinical trials for AD should be obtained across several domains of neurologic function, including cognition and functioning. After Week 105 of the OLE study, assessment frequency is reduced to minimize patient burden but continue efficacy monitoring. For details of the schedule of activities, see [Appendix 1](#).

3.4.6 Rationale for Pharmacokinetic Sampling

A sparse sampling schedule for serum concentrations of crenezumab is being utilized to minimize patient burden and yet still provide an adequate assessment of crenezumab exposure.

The serum PK data will be needed for interpretation of the ADA impact of pharmacokinetics and may be compared with available data from other crenezumab studies as well as for the assessment of exposure-response relationships for relevant imaging, plasma PD biomarkers, ECG, and efficacy and safety outcomes in patients with pAD to mAD, as appropriate.

Crenezumab concentration in CSF will be measured at Week 53 *only* in patients who were in the CSF longitudinal substudy (see Section [3.4.7.1](#)), *provided they consent to continue in the substudy during the OLE*. The CSF measurement will contribute to the longitudinal CSF substudy and the assessment of crenezumab partitioning into the CSF at 60-mg/kg Q4W dosing as well as of the exploratory exposure-response relationship between crenezumab concentration and CSF biomarkers.

3.4.7 Rationale for Biomarker, PET Assessments and MRI Assessments

The biomarker, PET, and MRI assessments described in Section [3.4.7.1](#) (CSF), Section [3.4.7.2](#) (PET imaging), and Section [3.4.7.3](#) (brain volumetry) will be used to investigate the effect of crenezumab on the underlying pathology of AD in the clinical trial population.

3.4.7.1 Cerebrospinal Fluid Biomarkers (for Patients Who Were in the BN29552 or BN29553 CSF Longitudinal Substudy Only)

Amyloid plaque deposition, neurofibrillary tangle formation, and neuronal degeneration are known pathologic features of AD. Decreased CSF A β_{1-42} and elevated CSF t-tau and p-tau are considered a biochemical signature of AD. Accumulating evidence suggests that low CSF A β_{1-42} reflects underlying amyloid plaque pathology, whereas increased t-tau and p-tau levels may be reflective of neurodegeneration and/or tau pathology.

The planned additional CSF assessment at Week 53 of the OLE study will contribute to the CSF longitudinal data collected in the substudy associated with Protocols BN29552 and BN29553 (CSF Longitudinal Substudy) and will be taken for patients who have completed the following:

- The CSF Longitudinal Substudy in either Study BN29552 or BN29553
- *Consented to additional CSF samples during the OLE study*

3.4.7.2 Positron Emission Tomography Imaging Assessment

The definitive postmortem diagnosis of AD requires the presence of progressive dementia during life and the presence of neuropathologic lesions (i.e., neuritic plaques composed of A β aggregates and neurofibrillary tangles formed from hyperphosphorylated tau protein). However, imaging approaches using ligands that demonstrate high affinity for aggregated amyloid are able to provide an assessment of deposition in vivo, which can be evaluated over time (Clark et al. 2011).

The planned additional PET imaging assessment will contribute to the substudies associated with Protocols BN29552 and BN29553, the Amyloid-PET Longitudinal Substudy and the Tau-PET Longitudinal Substudy and will be taken for patients who have completed the following:

- The Amyloid-PET Longitudinal Substudy and/or the Tau-PET Longitudinal Substudy for either Study BN29552 or BN29553
- *Consented to additional PET imaging assessments during the OLE study*

3.4.7.3 MRI Assessments for Brain Volumetry

A characteristic feature of AD is neuronal destruction. Such neuronal loss is demonstrated at a macroscopic level by progressive cerebral atrophy, which can be tracked on MRI (Fox and Kennedy 2009). Multiple changes in brain anatomy beyond those associated with normal aging have been reported in patients with AD (e.g., enlarged ventricles, decreased cortical thickness, decreased total brain volume, and hippocampal atrophy), and there is evidence for strong correlations between these imaging biomarkers and functional cognitive measures (Li and Wahlund 2011). On the basis of volumetric MRI measurements, the two most established markers of disease progression through longitudinal observational studies are hippocampal and whole brain atrophy (Fox et al. 2000, 2005; Jack et al. 2010), with ventricular expansion a third and related quantitative marker.

Therefore, to quantify the effects of crenezumab on neurodegeneration, whole brain volume, ventricular enlargement, and regional brain volume changes will be assessed at screening and following treatment with crenezumab. All MRI reads and volume measures will be conducted by the central reading facility.

4. **MATERIALS AND METHODS**

4.1 **PATIENTS**

Patients who completed the Week 105 study visit of Study BN29552 or BN29553 and meet the eligibility criteria are eligible to participate in this OLE study. Patients who discontinued the study prior to completion of the Week 105 visit will not be eligible for this OLE study.

Concomitant acute and chronic diseases (including significant laboratory abnormalities) should be monitored and treated towards treatment targets as per local guidance.

4.1.1 **Inclusion Criteria**

Patients must meet the following criteria for study entry:

- Previous participation in Study BN29552 or BN29553 and completion of the Week 105 visit.

Patients who discontinued from one of these studies prior to completion of the Week 105 visit are not eligible. Temporary halting of study drug (e.g., because of an adverse event) in Study BN29552 or BN29553 is not exclusionary.

- *Written informed* consent signed by the patient (co-signed by the patient's legally authorized representative if required by the local regulations, guidelines, and independent Ethics Committee [EC] or Institutional Review Board [IRB]) or the patient's authorized representative under applicable local law

In the course of the study, assessment of a subject's capacity to re-consent *should be done, and written informed re-consent signed by the patient* (co-signed by the patient's legally authorized representative if required by the local regulations, guidelines, or independent EC/IRB) or the patient's authorized representative should be *obtained*, as per applicable local law and requirements.

- *Every effort should be made* to have the same caregiver participate throughout the duration of the OLE study who also participated in Study BN29552 or BN29553.

The caregiver, in the investigator's judgment, should fulfill the following:

- Have frequent and sufficient contact with the patient to be able to provide accurate information regarding the patient's cognitive and functional abilities, agree to provide information at clinic visits (which require partner input for scale completion), sign the necessary consent form, and have sufficient cognitive capacity to accurately report upon the patient's behavior and cognitive and functional abilities.
- Be in sufficiently good general health to have a high likelihood of maintaining the same level of interaction with the patient and participation in study procedures throughout the study duration.

- If the caregiver cannot continue to participate in the OLE study and cannot be replaced, the patient can continue in the OLE so long as patient safety can be assured.
- Willingness and ability to complete all aspects of the study (including MRI, lumbar puncture [if applicable], and PET imaging [if applicable]).
 - The patient should be capable of completing assessments either alone or with the help of the caregiver.
- Adequate visual and auditory acuity, in the investigator's judgment, sufficient to perform the neuropsychological testing (eye glasses and hearing aids are permitted).
- For women of childbearing potential: agreement to remain abstinent (refrain from heterosexual intercourse) *or use contraceptive measures, and agreement to refrain from donating eggs, as defined below:*

Women must remain abstinent or use contraceptive methods that result in a failure rate of <1% per year during the treatment period and for at least 8 weeks after the final dose of study drug. Women must refrain from donating eggs during this same period.

A woman is considered to be of childbearing potential if she is postmenarcheal, has not reached a postmenopausal state (12 continuous months of amenorrhea with no identified cause other than menopause), and has not undergone surgical sterilization (removal of ovaries and/or uterus). *The definition of childbearing potential may be adapted for alignment with local guidelines or requirements.*

Examples of contraceptive methods with a failure rate of <1% per year include bilateral tubal ligation, male sterilization, established proper use of hormonal contraceptives that inhibit ovulation, hormone-releasing intrauterine devices, and copper intrauterine devices.

The reliability of sexual abstinence should be evaluated in relation to the duration of the clinical trial and the preferred and usual lifestyle of the patient. Periodic abstinence (e.g., calendar, ovulation, symptothermal, or postovulation methods) and withdrawal are not acceptable methods of contraception.

- For men: agreement to remain abstinent (refrain from heterosexual intercourse) or use contraceptive measures, and agreement to refrain from donating sperm, as defined below:

With a female partner of childbearing potential or pregnant female partner, men must remain abstinent or use a condom during the treatment period and for at least 8 weeks after the *final* dose of study drug to avoid exposing the embryo. Men must refrain from donating sperm during this same period.

The reliability of sexual abstinence should be evaluated in relation to the duration of the clinical trial and the preferred and usual lifestyle of the patient. Periodic abstinence (e.g., calendar, ovulation, symptothermal, or postovulation methods) and withdrawal are not acceptable methods of *preventing drug exposure*.

4.1.2 Exclusion Criteria

Patients who meet any of the following criteria will be excluded from study entry or continued participation:

- Patients who discontinued treatment permanently in Study BN29552 or BN29553 for safety reasons
- *Impaired coagulation (screening PT > 1.2 × the upper limit of normal (ULN) that remains abnormal on retest)*
- Evidence of more than 10 ARIA-H (microbleeds and/or leptomeningeal hemosiderin deposits) at the Study BN29552 or BN29553 Week 105 visit, as assessed by central review of MRI
- Diagnosed with three recurrent, symptomatic ARIA-E events or exacerbations of previous events
- Presence of intracranial lesion that could potentially increase the risk of CNS bleeding (e.g., intracranial aneurysm; arteriovenous malformation)
- At risk of suicide in the opinion of the investigator
- Alcohol and/or substance abuse or dependence (according to Diagnostic and Statistical Manual of Mental Disorders Version 5 criteria) within the past 2 years and during the study

Nicotine use is allowed.

Marijuana use is not allowed within the past 2 years.

- Inability to tolerate MRI procedures or contraindication to MRI, including, but not limited to, presence of pacemakers not compatible with MRI, aneurysm clips, artificial heart valves, ear implants, or foreign metal objects in the eyes, skin, or body that would contraindicate an MRI scan; or any other clinical history or examination finding that, in the judgment of the investigator, would pose a potential hazard in combination with MRI
- Pregnant or lactating, or intending to become pregnant during the study
- Any other severe or unstable medical condition that, in the opinion of the investigator or Sponsor, could be expected to progress, recur, or change to such an extent that it could put the patient at special risk, bias the assessment of the clinical or mental status of the patient to a significant degree, or interfere with the patient's ability to complete the study assessments
- Chronic use of anticoagulants or participation in any other investigational drug treatment trial

See Section 4.4 for further details and other concomitant medication restrictions.

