4.6 TREATMENT, PATIENT, STUDY, AND SITE DISCONTINUATION

4.6.1 Study Treatment Discontinuation

Patients must permanently discontinue study treatment if they experience any of the following:

- Pregnancy

- Evidence of more than 15 *ARIA-H* (microbleeds and/or areas of leptomeningeal hemosiderosis) including any present at baseline, as assessed by central review of MRI
- Diagnosed with three recurrent, symptomatic *ARIA-E* events or exacerbations of previous events

The primary reason for study treatment discontinuation should be documented on the appropriate eCRF. Patients who discontinue study treatment prematurely will not be replaced.

All patients who discontinue from the study treatment early will be asked to return at 4 and 16 weeks from the time of the last dose of study treatment for safety assessments. Patients that discontinue before Week 105 will also be asked to return for their next scheduled annual assessment (Week 53 or Week 105). If the next annual follow-up visit (Week 53 or *Week* 105) is expected within 3 months of the 4-week safety visit, the annual and 4-week safety visits can be combined.

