5.1.2.1 ARIA-E

Asymptomatic ARIA-E with Barkhof Grand Total Score < 4 (Barkhof et al. 2013):

- Continue study drug at the same dose (i.e., 60 mg/kg crenezumab)
- Repeat magnetic resonance imaging 4 weeks later
 - If ARIA-E is stable or decreased, continue study drug and monthly MRI monitoring until event resolves. Once ARIA-E completely resolves, conduct MRI monitoring as per Section [4.5.9](#).
 - If ARIA-E increases (Barkhof Grand Total Score ≥ 4) or symptoms develop, refer to the rule below.

Symptomatic ARIA-E (any size) or ARIA-E with Barkhof Grand Total Score ≥ 4 :

- Temporarily interrupt study drug and implement monthly MRI monitoring
- Once symptoms and ARIA-E resolve, reintroduce study drug at the same dose (i.e., 60 mg/kg crenezumab) and perform an MRI after 4 weeks of dosing. If no new ARIA-E is detected, MRI monitoring as per Section [4.5.9](#).

Any new onset of ARIA-E: Treat the same as the first event on the basis of symptoms and Barkhof Grand Total Score. However, **in the case where a patient is diagnosed with three recurrent, symptomatic ARIA-E events or exacerbations of previous events, permanently discontinue the study drug**. Implement monthly MRI monitoring until resolution of both symptoms and ARIA-E. As per the protocol, maintain the patient in the study until study end and perform assessments as per the schedule of activities.

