5.4.3 Reporting Requirements for Pregnancies

5.4.3.1 Pregnancies in Female Patients

Female patients of childbearing potential will be instructed to immediately inform the investigator if they become pregnant during the study or within 8 weeks after the *final* dose of study drug. A paper Clinical Trial Pregnancy Reporting Form should be completed and submitted to the Sponsor or its designee immediately (i.e., no more than 24 hours after learning of the pregnancy), either by faxing or by scanning and emailing the form using the fax number or email address provided to investigators. Pregnancy should not be recorded on the Adverse Event eCRF. The investigator should discontinue study drug and counsel the patient, discussing the risks of the pregnancy and the possible effects on the fetus. Monitoring of the patient should continue until conclusion of the pregnancy. Any serious adverse events associated with the pregnancy (e.g., an event in the fetus, an event in the mother during or after the pregnancy, or a congenital anomaly/birth defect in the child) should be reported on the Adverse Event eCRF. In addition, the investigator will submit a Clinical Trial Pregnancy Reporting Form when updated information on the course and outcome of the pregnancy becomes available.

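### The exclusion lead-in ends study participation for two events that other sections treat only as reasons to stop drug: three recurrent symptomatic ARIA-E events and pregnancy

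*Combined protocol and SAP*

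**What the plan says.** The lead-in in 4.1.2, repeated word for word in the synopsis, reads: "Patients who meet any of the following criteria will be excluded from study entry or continued participation". It therefore reaches beyond entry. At least one criterion is also written to run on study: substance abuse counts "within the past 2 years and during the study".

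The list includes three recurrent symptomatic ARIA-E events (or exacerbations), with no timepoint attached, and pregnancy. Other sections say what to do when these arise after entry:

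- **5.1.2.1 (ARIA-E).** Study drug stops permanently. Then: "Implement monthly MRI monitoring until resolution of both symptoms and ARIA-E". The site is also to "maintain the patient in the study until study end and perform assessments as per the schedule of activities".
- **4.6.1 (Study Treatment Discontinuation).** Under the words "Patients must permanently discontinue study treatment if they experience any of the following" it names pregnancy, more than 15 ARIA-H, and three recurrent symptomatic ARIA-E events. It continues: "All patients who discontinue from the study treatment early will be asked to return at 4 and 16 weeks", counted from the last dose. Those who stop before Week 105 are also asked back for the next annual visit.
- **5.4.3.1 (Pregnancies in Female Patients).** The investigator stops study drug. "Monitoring of the patient should continue until conclusion of the pregnancy".

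Sections 3.3, 3.4.2 and 5.1 and the off-treatment columns of Appendix 1 also provide for follow-up after the last dose.

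**The concern.** For the same ARIA-E event, 4.1.2 tells the site that the patient may not go on participating and 5.1.2.1 tells it to keep the patient in the study. Both cannot be followed. For pregnancy, the lead-in ends participation while 4.6.1 ends treatment and schedules further study visits.

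Long-term safety is the primary objective, and a patient with repeated symptomatic ARIA-E is one whose later course matters most to it. With about 350 centers, different sites could handle the same situation differently depending on which section they read. Section 9.2 does not allow prospective waivers of eligibility criteria. By inference, a site that correctly follows 5.1.2.1 could be told that it breached 4.1.2, and the reverse.

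**Working it through.** The main check is a comparison of text; the plan states no figure on this point to reproduce.

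**Step 1. Does participation mean dosing?** The protocol keeps the two apart. Section 4.6.1 deals with stopping study treatment and 4.6.2 with leaving the study. Section 3.1 describes parent-study patients who stopped treatment early yet stayed in the study. Read in that vocabulary, ending participation means leaving the study.

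**Step 2. Three recurrent symptomatic ARIA-E events.**
- 4.1.2 and synopsis: participation ends.
- 5.1.2.1: drug ends, MRI continues monthly until resolution, participation continues.
- 4.6.1: treatment ends, visits at 4 and 16 weeks and, before Week 105, the next annual visit.

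The event is described in the same terms in all three places, and the first instruction is the opposite of the second. This is a direct contradiction.

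**Step 3. Pregnancy.**
- 4.1.2 and synopsis: participation ends.
- 4.6.1: treatment ends, with the same follow-up visits as in Step 2.
- 5.4.3.1: drug ends, monitoring runs to the end of the pregnancy.

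The conflict rests on 4.6.1. Section 5.4.3.1 only supports it, because a pregnancy can be monitored after a patient has left the study.

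**Step 4. Which text governs?** I found no clause giving one section precedence. The specific sections agree on the question at issue: the patient stays under follow-up after drug stops. The intent is therefore clear and the lead-in is the outlier.

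**Step 5. How many patients?** Inputs: 4 patients with ARIA-E across the programme, 1 of them symptomatic (1.2.3); about 1051 people exposed (1.2.2); about 925 patients expected in this study (6.1).

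- Rate of any symptomatic ARIA-E: 1 / 1051 = 0.095%, exact (Clopper-Pearson) 95% CI 0.002% to 0.53%.
- Expected number: 925 × 1 / 1051 = 0.88, 95% CI 0.02 to 4.9.

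Three recurrent symptomatic events are a subset of this, so the expected number is about one or fewer. The rate is rough: the 1051 include healthy volunteers and people on lower doses, part of the data is still blinded, and exposure in this study may be longer. The documents give no pregnancy rate. Patients were aged 50 to 85 in the parent studies (1.2.2), so the number should be close to nil.

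**The case against.** The strongest reply is that the conflict does no harm by itself. A patient excluded under 4.1.2 has also stopped study drug, so 4.6.1 applies on its own terms and asks for the 4- and 16-week visits and, before Week 105, the annual visit. The Appendix 1 note asks for the early-termination assessments but does not say that only those are done. The only rule in 4.6.2 that ends follow-up is tied to withdrawal of consent. **This stands.** A reader might infer that the lead-in costs the patient the 16-week and annual visits, and leaves post-dose Weeks 4 to 16 without a visit at which new adverse events are collected. The documents do not support that as a consequence of the lead-in alone; the site would also have to disregard 4.6.1. Unscheduled MRI (4.5.9) and investigator follow-up of adverse events and pregnancies (5.5.1) remain available in any case.

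A reader might also infer that the lead-in has the wrong scope for other criteria that can arise on study: a lesion with bleeding risk, suicide risk, substance abuse, an MRI contraindication, or an unstable condition. No section contradicts the lead-in for these. Section 4.6.2 allows withdrawal when a medical condition puts the patient's safety at risk. Whether such patients should stay for follow-up is a design choice, not an error in the text.

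It can finally be said that the specific rule obviously prevails over the general one. That is the likely intent, but the protocol does not say so, and for ARIA-E two operative sections give opposite instructions. This part of the reply does not remove the point.

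**Conclusion.** The point holds, as a minor error of wording. The lead-in in 4.1.2 and the synopsis contradicts 5.1.2.1 and 4.6.1 for three recurrent symptomatic ARIA-E events and conflicts with 4.6.1 for pregnancy. Confidence in the textual conflict is high.

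The expected number of patients affected is about one or fewer, assuming that the programme's symptomatic ARIA-E rate carries over to this study. No bias is claimed. The finding does not extend to the other exclusion criteria.

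**What to change.** Leave the lead-in as it stands. In 4.1.2 and in the synopsis, add to the ARIA-E and pregnancy bullets:

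*If first met after entry, study drug is permanently discontinued but the patient remains in the study for follow-up per Section 4.6.1 (and Section 5.1.2.1 for ARIA-E, Section 5.4.3.1 for pregnancy).*

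In the second bullet the sentence should attach to pregnancy itself, because 4.6.1 does not list lactation or the intention to become pregnant.

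Replacing continued participation with continued study treatment for the whole list would go too far. It would, for example, also cover a patient who joins another investigational drug trial, which 4.4 prohibits.

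The cost is one sentence on two bullets, in two places, at the next amendment. It adds no procedure or visit type and leaves the existing stops of dosing untouched.
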